6 SUBJECT DISPOSITION

Disposition will be presented based on the FAS. The number of subjects enrolled/randomized, the number of subjects who received study treatment, the number of subjects who completed study treatment, and the number of subjects who completed the study will be reported separately by cohort and overall by treatment group using format as specified in [Table 5.4](#).

Disposition data will be listed for both the sentinels and randomized subjects by cohort and treatment group, and will indicate the investigator site. In addition, a listing will be provided for those subjects who were screen failures, along with the reason for screen failure.

7 DISCONTINUATION AND COMPLETION

For subjects who prematurely discontinued from the study, the primary reason for discontinuation will be summarized. A similar summary will be provided for subjects who discontinued study treatment.

The number of subjects who completed study treatment and the number of subjects who completed the study will be summarized by cohort and overall by treatment group using format as specified in [Table 5.4](#). All summaries will be based on the FAS.

Listing will be provided on the FAS.

8 PROTOCOL EXEMPTIONS AND DEVIATIONS

The number and percentage of subjects with any protocol deviation, any major protocol deviation, and any minor protocol deviation will be presented separately by cohort and overall by treatment group using format as specified in [Table 5.4](#), according to the categories described in the study specific protocol deviation plan. Reasons for major/minor deviations will be summarized. Subjects who received the wrong treatment will be identified after data base lock and considered as a Major Protocol Deviation.

All summaries will be based on the FAS.

All protocol deviations will be listed for sentinel and randomized subjects by cohort. sentinel/randomized subjects, treatment group, and subject ID. A separate listing of all major deviations which have been classified as a “Dosing Irregularity” will also be provided.

In addition, a summary and listing of COVID-19 specific protocol deviations will be provided.

9 DEMOGRAPHICS AND BASELINE CHARACTERISTICS

Demographic and baseline characteristics will be summarized for the FAS, and presented for by cohort by treatment group with the format as specified in [Table 5.1](#), [Table 5.2](#), and [Table 5.3](#) for Cohorts 1, 2, and 3, respectively and [Table 5.4](#) for Overall. Rules on standing height/body length and sitting height/crown to rump length are provided in [Section 14.1](#).

Demographics will be summarized as:

- Age at Screening (months with 1 decimal place)
- Age at Day 1 (months with 1 decimal place)
- Sex (Male, Female)
- Race (American Indian or Alaska Native, Asian [Japanese/Other], Black or African American, Native Hawaiian or Pacific Islander, White, Multiple, Not Provided Due to Patient Privacy Rules)
- Ethnicity (Hispanic or Latino, Not Hispanic or Latino)

Baseline characteristics will be summarized as:

- Weight (kg) and Weight Z-Score
- Body Mass Index (BMI) (kg/m^2), and also BMI Z-Score for subjects aged 24 months or older

Baseline growth measures will be summarized as:

- Height Z-Score (Refer to [Section 14.2.1](#))
- AGV (cm/yr)
- Standing Height/Body Length (cm)
- Sitting Height/Crown to Rump(cm)
- Lower Body Length (cm) = Standing Height - Sitting Height
- Head Circumference (cm)
- Upper Arm Length (cm)
- Lower Arm (Forearm) Length (cm)
- Arm Span (cm)
- Upper Leg Length (Thigh) (cm)
- Knee to Foot Height (cm)

- Tibial Length (cm)
- Upper to Lower Body Segment Ratio
- Arm Span to Standing Height Ratio
- Upper Arm Length to Lower Arm (Forearm) Length Ratio
- Upper Leg Length to Tibial Length Ratio

A listing of each sentinel and randomized subject's demographic/baseline data will be provided.

10 MEDICAL HISTORY

Medical history will be solicited from each subject, including all major illnesses, diagnoses, and surgeries that the subject has ever had; any prior or existing medical conditions that might interfere with study participation or safety; and evaluation for knee, thigh, hip or groin pain, or change in gait/activity.

All medical history terms will be coded in accordance with MedDRA Version 24.1 that each term is assigned a SOC and PT.

A list of PTs considered to be ACH-related will be reviewed prior to the data cut. A listing for the complete list of final terms will be generated, retained in the study file, and documented in the CSR.

All recorded medical history will be summarized on the FAS by SOC and by PT by cohort and overall by treatment group using format as specified in [Table 5.4](#), ordered by descending order of frequency of SOC in the overall population. In addition, achondroplasia-related medical history will be listed and summarized separately by SOC and PT in a similar manner.

The number of subjects with abnormal physical exam results at screening will be summarized and listed.

A listing of each subject's medical history will be provided, plus a listing of each subject's achondroplasia-related medical history.

11 PRIOR AND CONCOMITANT MEDICATIONS

Prior and concomitant medications will be summarized for the FAS. For analysis purposes, the following definitions will be used to determine prior and concomitant medications for the entire study period:

- Prior medications: Any medications taken and ended prior to the initial study treatment administration date will be considered prior medications.
- Concomitant medications: Any medications taken on or after the initial study treatment administration date up to 30 days after discontinuation of study treatment will be considered concomitant medications and included in summary tables. This also includes medications initially taken prior to the initial study treatment administration date but continued or ended on or after the initial study treatment administration date.

Concomitant medications will be summarized separately by cohort and overall by treatment group using format as specified in [Table 5.4](#), and a separate summary will be provided which includes only those concomitant medications that were initiated on study.

All medications will be coded using the latest version available within BioMarin of the World Health Organization Drug (WHO Drug) dictionary (Version September 2021). Prior and concomitant medication use will be separately summarized by Anatomical Therapeutic Chemical (ATC) medication class (Level 2) and preferred name (i.e., generic medication name). If a medication doesn't have ATC level 2, they are grouped as "ATC Level 2 classification unavailable". A subject reporting the same medication more than once will be counted once when calculating the number and percentage of subjects who received that medication. A listing of prior and concomitant medications will be provided. In addition, a listing for COVID vaccine will be provided.

12 COMPLIANCE

Treatment compliance will be calculated based on the study treatment preparation and study treatment administration records captured in the eCRF, and summarized separately by cohort and overall by treatment group using format as specified in [Table 5.4](#) for the safety population.

For each subject it considers all data up to the last recorded dose. For each column, results will be separated for 15 µg/kg, 30 µg/kg, and overall.

For each daily injection, the amount of study treatment taken will be calculated based on the number of units in the syringe pre-injection, minus the number of units remaining in the syringe post-injection. For the cases that the number of units in the syringe pre-injection is not captured in the eCRF, if response to “Was study drug administrated?” is “Yes”, then it will be assumed to be the same as the planned dose; if response to “Was study drug administrated?” is “No”, then it will be assumed to be missing and these records will not be included in the compliance calculation.

The total amount of study treatment taken will be calculated based on the amount of study treatment taken (units) in the corresponding treatment duration.

The total amount of study treatment planned is determined based on the duration of treatment and the planned dose per day.

Percentage compliance for each subject will be derived from the total amount of study treatment intake divided by the planned study treatment intake, and multiplied by 100:

$$\text{Treatment Compliance (\%)} = \frac{\text{Total Amount of Study Drug Taken (units)}}{\text{Total Amount of Study Drug Planned (units)}} \times 100$$

Treatment compliance will be calculated and summarized separately by cohort and overall by treatment group using format as specified in [Table 5.4](#). For each column, results will be separated for 15 µg/kg, 30 µg/kg, and overall.

- Compliance with protocol-specified treatment regimen (%)
- Compliance with protocol-specified treatment regimen (≥50%, ≥60%, ≥70%, ≥80%, ≥90%, ≥100%, ≥110%, ≥120%)

Listings will be provided for compliance.

13 EXTENT OF EXPOSURE TO STUDY TREATMENT

Dosing information is recorded by subjects in the paper diary and also by the site on visit days. In the case of duplicate records with the same date, if the investigator confirms the date, then investigator reported dosing data will be used. All summaries will be produced based on the safety population, and presented separately by cohort and overall by treatment group using format as specified in [Table 5.4](#). For each column, results will be separated for 15 µg/kg, 30 µg/kg, and overall.

Descriptive statistics will be provided for the following variables:

- Duration of treatment (days)
= Date of last dose – Date of first dose + 1
- Total number of doses administered
= Number of doses administered between date of Day 1 and date of last dose
- Total number of doses missed
= Number of doses missed between date of Day 1 and date of last dose
- Total amount of weight adjusted dose administered (µg/kg) by planned dose
- Average weight-adjusted daily dose administered (µg/kg/day) by planned dose

The frequency and percent of subjects will be provided for the following variables, where missed doses are counted between the date of first dose (Day 1) and date of last dose:

- Number of subjects who missed at least one dose
- Number of subjects who missed more than one dose
- Number of subjects who missed more than 5 consecutive doses
- Number of subjects who missed more than 10 consecutive doses

The frequency and percent of events will be provided overall for the following variable:

- The total number of missed doses and reason for each missed dose (Site Error, Parent/Caregiver Error, Home Health Error, Adverse Event, Other, Missing) will be provided.

A listing of each subject's extent of exposure by planned dose 15 µg/kg and 30 µg/kg will also be provided.

14 EFFICACY EVALUATIONS

14.1 General Approaches for Analyzing Growth Parameters

All growth parameters assessed by anthropometric measurements are measured at Baseline, Day 1, Week 6, Week 13, Week 26, Week 39, Week 52, and early termination visit.

Growth parameters are measured 3 times for each assessment. It is the mean of these 3 assessments that are considered for the summaries and analyses. In the event that all 3 are not available, the mean of the 2, or the individual assessment is taken. All measures and means of the measures will be included in the listings.

The general rule when summarizing height (standing and sitting) is that standing height/sitting height will be used if subjects ≥ 24 months, body length/crown to rump will be used if subjects < 24 months. For subjects with both sets of measurements available, like to like will be used based on their measurements available for their age at baseline.

Thus, in general, for subjects in Cohort 1 standing height and sitting height will be summarized. For subjects in Cohorts 2 and 3 body length and crown to rump will be summarized. If body length is not measured and standing height is available, standing height will be used. If both sets of measures are available, like to like will be used based on their measurements available for their age at baseline.

These rules will impact the following growth endpoints: standing height/body length Z-Score, standing height/body length, AGV, sitting height/crown to rump, lower body length, arm span to height ratio, upper to lower body segment ratio, BMI, and BMI Z-Score.

BMI Z-Score will only be derived for subjects aged 24 months or older.

Body length and crown to rump will not be summarized separately but integrated within the summaries for standing height and sitting height. Body length and crown to rump are however provided separately in a listing.

Appendix [25.1](#) provides details of the derivations used for each endpoint.

All efficacy endpoints will be assessed using the FAS.

Visit windows are applied for all assessments (see Section [5.4](#)) and are used to summarize the growth measures by visit.

All parameter assessments are considered for inclusion in analyses.

With the exception of AGV (see Section 14.3.2), summary tables for all growth measures including standing height/body length Z-Score, standing height/body length, upper to lower body segment ratio, body proportion ratios, other growth measures (see Section 14.3.5), BMI, BMI Z-Scores, and weight Z-Scores will include assessments at baseline, Week 26 and Week 52 from Study 111-206, and 6 months prior in Study 111-901. For subjects in Cohort 3 assessments at 3 months prior to baseline in Studies 111-206 or 111-901 will be included.

Each table will include summaries of the absolute observed measures and its change from baseline at each of these time points. The tables will summarize data separately by cohort by treatment group using format as specified in Table 5.1, Table 5.2, and Table 5.3 for Cohorts 1, 2, and 3, respectively.

ANCOVA models will be conducted for change from baseline at Week 52 in standing height/body length Z-Score, standing height/body length, AGV, and upper to lower body ratio for all cohorts overall and/or by cohort, as appropriate. Unless otherwise specified, all models will include the following baseline covariates: randomization age stratum, age at baseline, baseline AGV, and sex. Analyses of standing height/body length Z-Score, standing height/body length, and upper to lower body ratio will include their baseline as additional covariate.

For the model-based analyses, if the required assessment at Week 52 is missing but there are assessments before and after Week 52, a linear interpolation using the measurements closest to the before and after Week 52 will be used, otherwise those with no assessment after Week 52, multiple imputation by using placebo data from subjects in the same cohort (PROC MI) will be used to impute the missing values for standing height/body length and upper to lower body segment ratio at Week 52.

In addition to the primary analyses conducted on FAS, sensitivity analyses will also be conducted and are described in Section 14.2.

Results of the statistical analyses will be provided in separate tables, including the least-squares (LS) mean change from baseline at Week 52 for each treatment group, the treatment difference in LS means (calculated as vosoritide - Placebo), the 95% confidence interval (CI) for the treatment difference, and corresponding 2-sided p-value.

Listings for standing height/body length and standing height/body length z-score will include all assessments (i.e., all measures and means of the measures) and spaghetti plots for height and height Z-Score will include assessments every 6 months and will be ordered by cohort,

sentinel/randomized subject, treatment, subject ID and visit date including 111-901 and 111-206.

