All sentinel and randomized subjects in Cohort 1 received 15 µg/kg dose. Sentinel subjects in Cohort 2 initially received 15 µg/kg dose and the dose was escalated to 30 µg/kg while they remained < 24 months of age following review of PK data as per protocol. All randomized subjects in Cohort 2 will receive 30 µg/kg dose while they remained < 24 months of age. All sentinel and randomized subjects in Cohort 3 received 30 µg/kg dose while they remained < 24 months of age. The dose for all sentinel and randomized subjects in Cohorts 2 and 3 will be adjusted to 15 µg/kg/day after they turn 24 months old.

The 111-206 study design is presented in [Figure 4.2.1](#). All subjects who complete the 111-206 study will be eligible to receive vosoritide in the extension study 111-208 after the Week 52 visit.

Figure 4.2.1: Study Design

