The analysis windows for assessments in 111-206 are defined in Table 5.4.2. The analysis windows are designated to be consecutive for scheduled visits to accommodate delayed visits due to impact of COVID-19. The upper bound of each visit window will be target day plus half of the difference between the current target day and the next target day, and the lower bounds of the window will be the upper bound of the previous window plus 1 except for Day 1, Day 2, Day 3, and Week 52. Lower bound, upper bound, and target date are the same for Day 1, Day 2, and Day 3. The upper bound of Week 52 will be target day plus 42 days. If there are two or more assessments within a designated window, the assessment that is closest to the target day will be used for analyses. If the two closest assessments to the target day are equidistant from the target day, the assessments taken on a scheduled visit per case report form (CRF) page will be used; if both are scheduled visits but not on the same day, the latest assessments will be used; if both are on the same day, the average of the assessments will be used. Unless otherwise specified, all analyses are based on derived visits.

Table 5.4.2: Visit Windows for Observed Assessments in 111-206

Derived Visit	Target Day ^a	Analysis Window ^a
Baseline		The last assessment prior to the first dose of study treatment unless otherwise specified.
Day 1	Day 1	Day 1
Day 2	Day 2	Day 2
Day 3	Day 3	Day 3
Day 8	Day 8	Day 4 - 15
Week 3	Day 22	Day 16 - 33
Week 6	Day 43	Day 34 - 68
Week 13	Day 92	Day 69 - 117
Week 20	Day 141	Day 118 - 162
Week 26	Day 183	Day 163 - 229
Week 39	Day 274	Day 230 - 320
Week 52	Day 365	Day 321 - 407

^a Target days and analysis windows are relative to Day 1 date defined in Section 5.3.

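### SAP Section 14.1 does not say which study, or which treatment, the post-Week 52 measurement used for interpolation may come from, so on-vosoritide growth can reach a placebo child's Week 52 value

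*SAP*

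**What the plan says.** All references are to SAP Version 2 (02 February 2022).

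- **Trigger and rule (Section 14.1).** Interpolation applies "if the required assessment at Week 52 is missing but there are assessments before and after Week 52"; then "a linear interpolation using the measurements closest to the before and after Week 52 will be used". Neither clause names a study or a treatment condition for the later measurement.
- **Fallback (Section 14.1).** With no assessment after Week 52, "multiple imputation by using placebo data from subjects in the same cohort (PROC MI) will be used".
- **Scope (Section 14.1).** "All parameter assessments are considered for inclusion in analyses".
- **Schedule (Section 14.1).** Growth parameters are "measured at Baseline, Day 1, Week 6, Week 13, Week 26, Week 39, Week 52, and early termination visit". Nothing later is listed.
- **Window (Section 5.4).** "The upper bound of Week 52 will be target day plus 42 days", so Week 52 covers Days 321 to 407. The windows were made consecutive "to accommodate delayed visits due to impact of COVID-19".
- **After the trial (Section 4.2).** "All subjects who complete the 111-206 study will be eligible to receive vosoritide in the extension study 111-208 after the Week 52 visit".
- **Estimand (Section 14.2.1).** The intercurrent-event text covers rescue medication and treatment discontinuation. It does not mention vosoritide started in the extension.

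**The concern.** The rule comes first in the handling of missing Week 52 data in the primary model-based analysis, and the key secondary endpoints are analysed by the same methods. Within 111-206 there is almost no measurement that could serve as the later point. The natural remaining source is the extension, where a former placebo child may be on vosoritide. A straight line from a Week 26 or Week 39 height on placebo to an on-drug height assigns part of the on-drug growth to the placebo year.

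The rule can also treat like children differently. A placebo child with no later height is imputed from placebo data, while an otherwise identical child with a 111-208 height can receive a value built partly on vosoritide growth. At stake is a placebo mean that is slightly too high and a treatment effect that is slightly too small.

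**Working it through.** **1. Where the later measurement can come from.** The Week 52 window follows from the SAP's own rule. Lower bound: 274 + (365 - 274)/2 = 319.5, taken as 320 for the end of Week 39, plus 1 = 321. Upper bound: 365 + 42 = 407. A height on Days 321-407 is itself the Week 52 value, so interpolation needs a height after Day 407. Two sources remain: a very late or unscheduled 111-206 visit, with the child still on blinded treatment, or a 111-208 visit.

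**2. Error for one affected placebo child.** Let t1 be the day of the last height before Week 52, t2 the day of the first height after the window, ts the first day of vosoritide in 111-208, and D the extra growth per year on vosoritide. With constant velocity within each treatment period,

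error / D = [(365 - t1)/(t2 - t1)] × [(t2 - ts)/365.25].

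The t1 values are SAP target days (Week 26 = 183, Week 39 = 274). The values of t2 and ts are assumptions, because the 111-208 schedule is not in the SAP.

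| t1 | t2 | ts | Calculation | Error / D |
|---|---|---|---|---|
| 274 | 456 | 365 | 0.500 × 0.249 | 0.125 |
| 274 | 547 | 365 | 0.333 × 0.498 | 0.166 |
| 183 | 456 | 365 | 0.667 × 0.249 | 0.166 |
| 183 | 547 | 365 | 0.500 × 0.498 | 0.249 |
| 274 | 456 | 407 | 0.500 × 0.134 | 0.067 |
| any | later height before first 111-208 dose | - | - | 0 |

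A first later height beyond Day 547 would give more (0.332 for Days 183 and 729), but that requires a child with no height for 546 days.

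**3. Effect on the estimate.** If a share p of placebo children is affected, the placebo mean rises by about p × error, and the vosoritide-placebo difference falls by the same amount. With p assumed at 5-15% and dosing from Day 365:

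- low: 0.05 × 0.125 = 0.6% of D;
- high: 0.15 × 0.249 = 3.7% of D.

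By head count, at least 27 + 17 + 17 = 61 children are randomised 1:1, so about 30 receive placebo. One affected child moves the pooled placebo mean by 0.125/30 = 0.4% to 0.249/30 = 0.8% of D. In Cohort 2 or 3, with about 8 placebo children, one child moves the cohort mean by 0.125/8 = 1.6% to 0.249/8 = 3.1% of D.

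These shares are on the height scale. They carry over to the Z-score approximately, if height is interpolated and then converted at the Week 52 age.

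**The case against.** The strongest reply is that the SAP never says 111-208 heights will be used. Where it brings in growth data from outside 111-206, it names 111-901 (Sections 5.4, 14.1, 14.2.1 and 14.3). Pooling with 111-208 appears only in Section 4.7, for two past informal interim analyses in which no efficacy data were analysed for randomised subjects. A reader might infer that the plan puts on-drug growth into the placebo arm. The text does not support that: it leaves the source open. What stands against the reply is that 111-208 is not excluded either, and that if only 111-206 data were meant, the rule would have almost nothing to act on.

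Second, the delay that the SAP anticipates is harmless. If a COVID-delayed Week 52 visit falls after Day 407, that visit is the closest later height, and it precedes extension dosing. This stands, and it is why the range starts at 0. Contamination needs a placebo child who enters 111-208 without a usable height on Days 321-407 and whose first later height follows dosing. Section 21 foresees missed visits and visits changed to virtual or home, so this is possible, but the SAP gives no basis for its frequency.

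Third, there are partial checks. The per-protocol set (Section 5.1.2) requires a Week 52 height within the protocol window, so it drops interpolated children. Sensitivity analysis (2) in Section 14.2.2, on subjects with no missing Week 52 data, probably drops them too, but the SAP does not say whether an interpolated value counts as missing.

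A reader might also suppose that the vosoritide arm is wholly free of any break at Week 52. That is not established: children are only eligible for 111-208, and in Cohorts 2 and 3 the planned dose changes at 24 months.

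**Conclusion.** The point holds as a gap in the rule. Section 14.1 fixes neither the study nor the treatment status of the later measurement. Applied literally to a 111-208 height taken after dosing, it carries vosoritide growth back into a placebo Week 52 value. The estimand does not cover this, because vosoritide started in the extension is neither rescue medication nor treatment discontinuation.

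The size is small: 0 to about 0.25 of the annual effect per affected placebo child, and at most about 4% of the estimated effect overall. Those figures rest on assumed extension heights at Day 456 or 547, dosing from Day 365, constant velocity within each period, and 5-15% of placebo children affected. The bias runs against vosoritide, so the gap does not threaten a false claim of efficacy. It deserves correction because it sits in the primary analysis and one sentence removes it.

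**What to change.** In Section 14.1, state that for placebo-randomised subjects only heights taken before the first vosoritide dose in 111-208 may serve as the later measurement, and that placebo subjects without such a height go to the same-cohort placebo-based multiple imputation already specified there. A late 111-206 visit on blinded treatment stays usable. In Section 14.2.2, state that interpolated values count as missing in the analysis of subjects with no missing Week 52 data.

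With this restriction the contamination is 0 by construction. The cost is two sentences and no new programming method. A few placebo values move from interpolation to multiple imputation, and the eligibility of the later height is judged differently by arm, which the SAP should acknowledge.
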